Once processed, vocal features are extracted from the audio and inputted into the neural network models. The software interprets the acquired signals using signal processing and an artificial neural network to quantitatively evaluate voice characteristics for presence of indicators correlated to depression and anxiety. The Kintsugi Voice Device then generates an output for signs of depression and anxiety which is displayed to the Device Operator. The Kintsugi Voice Device output will be positive for depression or negative for depression and positive for anxiety or negative for anxiety. The outcome can also be “uncertain” or within an “indeterminate range” if the Device cannot provide a high-confidence result.

Study Objectives

This study seeks to evaluate the ability of the Device to aid clinical assessment for depression and anxiety by comparing its output with the established diagnostic standard consisting of a diagnosis made by a specialist clinician based on DSM-5 criteria.

This is a prospective study of up to 100 subjects, ages ≥ 22 years of age.

We are striving for a 50%/50% split of subjects who have depression and/or anxiety and subjects who do not have depression and/or anxiety.

Study Endpoints

Effectiveness Endpoints

The primary endpoints of this study are to:

1. Determine the specificity and sensitivity of the Device in discriminating the presence of a significant depressive episode using the Structured Clinical Interview for DSM-5 Clinical Trial Version as the established diagnostic standard (“gold standard”)
2. Determine the specificity and sensitivity of the Device in discriminating the presence of a clinically significant anxiety state using the SCID-5-CT as the established diagnostic standard

The secondary endpoints of this study are:

- Measurement of the percentage of all adults for whom the Device provided no result
- Determine the specificity and sensitivity of the Device in discriminating the presence of a significant depressive episode compared to the PHQ-9
- Determine the specificity and sensitivity of the Device in discriminating the presence of a clinically significant anxiety state compared to the GAD-7

Safety Endpoints

Adverse events (AEs) and serious adverse events (SAEs) will be collected and reported from enrollment, which is determined by informed consent signature, through the completion of the study.

Study Duration

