The study is expected to last up to 8 months. The duration of each individual subject’s involvement in the study will be approximately 2 hours total consisting of a screening call followed by a psychiatrist clinical evaluation and online survey. However, participants could be active on the study for up to 2 weeks to schedule a SCID assessment.

Study Design and Procedures

This is a prospective fully remote, decentralized clinical study to measure the sensitivity and specificity of the Device predictions against clinical ground truth for major depressive disorder and for generalized anxiety disorder. Up to 100 participants will undergo investigational and comparator assessments for major depressive disorder and a clinically significant anxiety state.

The research coordinator will schedule a time with the participant for the evaluation. There will be a two-part evaluation: a web-based study survey and a specialist clinician evaluation via the SCID assessment. The SCID assessment will include questions about the past medical history of the participant as well as questions from the Clinical Global Impression - Severity scale. The order of the two evaluations will be randomized to minimize any potential bias.

The Device output will be positive for depression, negative for depression, or indeterminate for depression and positive for anxiety, negative for anxiety, or indeterminate for anxiety. PHQ-9 and GAD-7 scores will also be collected through the Study Survey.

Participants will also be evaluated by a specialist clinician via the SCID assessment. The psychiatrist performing the SCID assessment will be a board-certified psychiatrist. The clinical evaluation via the SCID assessment will be recorded and the channel-separated audio file of the participant during this assessment will be used as the Device input. The input for the Device will be obtained by the clinical research team and will be at least one minute of audio taken from the SCID assessment where the participant is asked about their current illness history and treatment history. The results of these assessments will act as the clinical comparator for comparison with the Device output.

Clinicians and participants will both be blinded to the participant the Device output and the participant assessment results (SCID, PHQ-9, GAD-7). Further, a SCID reviewer may review the recorded SCID assessment and standard clinical assessment and completed SCID template to minimize interrater variability.

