Subject Identification and Recruitment, Process of Consent

Subjects may be recruited through various mediums including but not limited to social media, Craigslist, and/or specialized clinical trial recruitment groups. At the time of enrollment, the mental status of the participant will not be known. Subjects may be recruited from populations that self-select as interested in mental health. Potential subjects will be provided with detailed study information so that they are able to make an informed decision.

If subjects wish to enroll, they will need to answer brief pre-screening questions about the inclusion/exclusion criteria to determine if they meet the study inclusion/exclusion criteria. Subjects ineligible for the study will be told they do not qualify. Subjects eligible for the study will receive an informed consent form if they are interested in participating. Participant identity will be verified before enrollment.

Participants will then schedule a time for the SCID assessment and to take the web-based study survey within the same day. Study participants can choose to end participation in the study at any time. The clinical research coordinator will also answer any questions on the study that participants have prior to enrollment.

Participants will also provide basic information such as their physical address, emergency contact, age, and email. Only the necessary participant information and medical history required for the study will be collected.

Recruitment will continue until up to 100 participants have SCID results or until the Sponsor terminates the study. The Sponsor may collate interim results at any time during the study to determine whether the study should continue.

[figure not shown]
Process of Consent

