- Presence of voice disorders that may impact vocal cords such as acute or chronic laryngitis, vocal cord paresis or paralysis, or spasmodic dysphonia
- Any known history of vocal cord injury or cerebrovascular accident or head trauma with residual dysarthria in the past year
- Past or active heavy smokers if there is impact on the vocal cords
- Any known history of congenital deafness
- Subjects who do not speak English
- Subjects who do not live in the United States
- Subjects who have previously participated in any Kintsugi-sponsored study.

Data Collection and Storage

Data will be retained in accordance with federal and institutional policies. Participants will be assigned a unique participant ID for de-identification. All data for analysis will be identified by participant ID number instead of personal identifiable information (PII).

The recruitment data with participant names, phone numbers, emails, location, and emergency contact will be password protected and only accessible to the research team.

Authorized representatives of institutions participating in the study, the Sponsor, the reviewing IRB and other groups or organizations that have a role in the study including reviewers of the structured interviews, regulatory bodies (e.g. the US Food and Drug Administration (FDA), Department of Health and Human Services (DHHS) agencies) will have access to and may view a participant's study information. They will be subject to regulations protecting patient confidentiality (e.g. HIPAA).

The data repository for this study includes:

- Device input
 - Voice sample provided as an audio recording
- Device output
- Video recording of the diagnostic assessment for clinically significant depression and clinically significant anxiety according to the DSM-5 criteria (SCID)
- Results from the PHQ-9 and GAD-7 questionnaire participant self-assessment
- Medical history relevant to the inclusion/exclusion criteria

At the conclusion of the study, the data will be retained in accordance with institutional policy. Identifiable data will be kept for 7 years after the completion of the study. De-identified data will be kept indefinitely.

Potential Risks and Benefits

Potential Risks

Risks related to the study are minimal.

The main potential risk to study participants is loss of confidentiality. Measures to protect the confidentiality of study participants will be implemented as described in the Data Collection and Storage section.

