Investigator(s) and research staff will be invited to participate in the study based on their medical specialty and experience conducting clinical research studies. Specialists will have board certification in psychiatry and have at least two years of experience diagnosing depressive and anxiety disorders.

Training and Monitoring

Investigator(s) and research staff, including clinical research coordinators and clinicians, will be trained on the study procedures. Clinicians administering the assessment will also receive training for the SCID to minimize discrepancies in scoring.

Informed Consent

An IRB-approved informed consent document will be provided to subjects through an electronic signature software tool. Subjects must sign the informed consent document before they can participate in the Study Survey or participate in a clinician evaluation. Clinical research coordinators will inform the subjects on the purpose of the study, expected duration, potential risks and benefits from the study, as well as making it clear that participants are free to refuse participation in this clinical study.

Participant Withdrawal Criteria

Participation in this study is voluntary and participants can withdraw from the study at any time. In order to withdraw, a participant will need to:

1. Call or email the research coordinator.
2. Let the research coordinator know about their intention to withdraw.

A participant that withdraws from the study prior to completion of study will not be paid.

A subject will be considered lost to follow up after 2 unsuccessful attempts to contact the subject.

If a participant withdraws from the study prior to its completion, their data will not be deleted; they will still be used for the research study.

Protocol Amendments

Any amendments to this study protocol must be communicated clearly in writing, signed, and dated by the sponsor and the principal investigator. IRB approval will be obtained for all study amendments.

Study Discontinuation

The study Sponsor has the right to terminate this study at any time.

Subject Confidentiality

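### The protocol lets the Sponsor use unspecified interim results at any time to decide whether to continue, and nothing in it rules out a stop when Device accuracy looks good

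*Protocol*

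**What the plan says.** All of this is in the protocol.

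- **Interim review** (Subject Identification and Recruitment, Process of Consent): "The Sponsor may collate interim results at any time during the study to determine whether the study should continue". The term for what is collated is not defined, and no schedule, statistic, threshold or independent reviewer is named.
- **End of recruitment** (same section): "Recruitment will continue until up to 100 participants have SCID results or until the Sponsor terminates the study".
- **Sample size** (Study Objectives): "This is a prospective study of up to 100 subjects". Study Design and Procedures, Study Population and the Data Analysis Plan also give 100 only as an upper limit. No section gives a minimum.
- **Termination** (Study Discontinuation): "The study Sponsor has the right to terminate this study at any time".
- **Blinding** (Study Design and Procedures): "Clinicians and participants will both be blinded to the participant the Device output and the participant assessment results". The Randomization section likewise withholds results from clinicians and participants. Neither mentions the Sponsor.
- **Access** (Data Collection and Storage): "Authorized representatives of institutions participating in the study, the Sponsor, the reviewing IRB" and other bodies "will have access to and may view" a participant's study information. The repository listed there holds Device output, the SCID recording, and PHQ-9 and GAD-7 results.
- **Primary endpoints** (Effectiveness Endpoints): sensitivity and specificity against the SCID, for depression and for anxiety, so four values. No performance goal is stated.

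**The concern.** The interim sentence is a written permission that ties results to continuation. It is more than a detail left open for the SAP. Combined with a ceiling in place of a planned number, a free right to terminate, and no barrier between the Sponsor and the Device-versus-SCID comparison, it leaves the final sample size open to being chosen in the light of accuracy.

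If that happened, high sensitivity and specificity would be reported more often than at a fixed 100, and they would rest on few cases. A reader would see that the study ended below 100, but the protocol does not require the reason to be reported.

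**Working it through.** The protocol states no alpha, power, performance goal or sample-size derivation, so there is no figure to reproduce. The check has two parts: whether the text bars a stop on accuracy, and what such a stop would do.

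**1. Does anything bar it?** The interim sentence limits neither content nor timing. The recruitment rule and the termination clause allow any final number up to 100. The blinding statements do not reach the Sponsor, and the access statement does. No passage closes the gap.

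**2. Illustration by simulation**, 40,000 runs of 100 participants.

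- From the protocol: ceiling of 100; up to 20% indeterminate results (glossary), with the upper figure used.
- Assumed: true sensitivity = specificity = 0.70 or 0.75; target 0.80; looks at 30, 40, …, 100; prevalence 50% per condition; disease, indeterminate status and correct calls each linked between conditions by a latent Gaussian correlation.
- Rule: stop at the first look where all four observed values are at least 0.80, otherwise run to 100. Indeterminates are excluded.

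The 50% per condition is an assumption. The 50/50 aim in Study Objectives is for depression and/or anxiety. At 50% each and independent, the share with either would be 1 − 0.5² = 75%; at 35% each, 1 − 0.65² = 58%.

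Chance that all four values are reported at 0.80 or above, fixed 100 → with looks:

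| Correlation | Truth 0.70 | Truth 0.75 |
|---|---|---|
| 0 | 0.01% → 0.6% | 0.3% → 4.9% |
| 0.5 | 0.03% → 1.5% | 0.8% → 7.5% |
| 0.8 | 0.06% → 2.5% | 1.4% → 10.6% |
| Conditions identical (same as one condition alone) | 0.7% → 10.5% | 6.3% → 27.3% |

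Sensitivity to the assumptions:

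- Only three looks (50, 75, 100), correlation 0.5: 0.3% (truth 0.70) and 3.3% (truth 0.75).
- Other targets, looks every 10, correlation 0.5. Truth 0.70: 8.3% at target 0.75 (about 1% at fixed 100) and 0.14% at 0.85. Truth 0.75: 0.85% at 0.85 and 0.12% at 0.90.
- Prevalence 35% each, independent: 0.01% → 0.7% (truth 0.70) and 0.4% → 5.1% (truth 0.75).

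Mean bias over all runs is +0.1 to +0.8 points in the four-value case and at most +1.9 points for one condition. Clopper-Pearson 95% intervals cover about 97% with looks.

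Early stops in the four-value case at target 0.80: median total 30 to 40 participants. At 50% prevalence they rest on a median of 13 to 15 scorable SCID-positives per condition, with mean reported sensitivity 0.86 to 0.87 and median exact lower limit 0.56 to 0.60. At 35% prevalence there are about 10 positives and the lower limit is about 0.52.

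**3. Precision by stopping point.** Expected scorable positives = N × prevalence × (1 − 0.20).

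- N = 30, 50%: 30 × 0.5 × 0.8 = 12. For 10/12 = 0.83, exact 95% interval 0.52 to 0.98.
- N = 30, 35%: 30 × 0.35 × 0.8 = 8.4, about 8. For 7/8 = 0.88, interval 0.47 to 1.00.
- N = 100, 50%: 100 × 0.5 × 0.8 = 40. For 34/40 = 0.85, interval 0.70 to 0.94.

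**The case against.** The strongest reply is that the feared use is not written. The protocol does not define interim results, names no accuracy criterion, and deciding whether to continue is just as natural for futility, feasibility or safety. Rules for looks are commonly left to a SAP, which is not shown and might confine the sentence. That stands against any claim of intent. It does not remove the point, because the protocol grants an open-ended permission without referring to a SAP, so a later rule would sit beside it.

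Two stronger readings are tempting and not supported:

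- *That the Sponsor is declared unblinded.* The protocol does not say so. It is an inference from blinding that names only two groups and from record access that the IRB and regulators share and that is ordinary for oversight.
- *That the error rate is inflated.* With no test, alpha or performance goal stated, there is nothing to inflate.

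The objection that the harm is modest also stands in large part. Mean bias is small, exact intervals keep their coverage and would show the imprecision, and the larger probabilities need one condition alone or identical conditions. Target, schedule and true accuracy are all assumed.

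**Conclusion.** The point holds as a permission that the protocol fixes badly. It is no evidence of a plan to stop on good results. Looking raised the chance of a favourable report in every scenario computed, but the size depends on the assumed rule: with all four values required, eight looks and correlation 0.5, from about 0.8% to 7.5% at truth 0.75 and from about 0.03% to 1.5% at truth 0.70. With fewer looks or a higher target it is smaller.

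The damage would lie in the timing and thinness of the headline estimate. An early stop would leave roughly 10 to 15 scorable positives per condition and a lower limit near 0.52 to 0.60, where a full 100 would give about 40 positives at 50% prevalence. This is worth correcting because correction is cheap; it does not invalidate the design.

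**What to change.** 1. Replace the interim sentence in the recruitment section with: *Until the last SCID is complete and data are locked, interim review is limited to accrual, SCID-positive counts, audio-sample repeats and adverse events; Device output will not be compared with SCID, PHQ-9 or GAD-7 except as prespecified in the statistical analysis plan.* SCID-positive counts stay available to steer the 50/50 aim.
2. State 100 as the planned number consistently in Study Objectives, Study Design and Procedures, the recruitment section, Study Population and the Data Analysis Plan, within the existing enrolment limit.
3. Add to Study Discontinuation: *If the study ends below 100 participants with SCID results, the N, the reason, and whether any Device-versus-SCID comparison had been seen will be reported.*

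One detail to settle while editing: a secondary endpoint is "Measurement of the percentage of all adults for whom the Device provided no result", and the protocol does not say whether unscorable audio counts towards it. Reviewing audio repeats may therefore overlap with that endpoint.

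The cost is one sentence replaced, one added and the wording of the sample size aligned. The Sponsor gives up unplanned accuracy looks, including informal futility looks, but keeps its right to terminate and its record access. Because participants count as enrolled at consent and enrolment is capped at 100, dropouts may leave slightly fewer than 100 with SCID results; this would simply be reported.

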Participants may feel discomfort answering questions or being interviewed.

An emergency contact will be collected for each participant, in the rare case that there is imminent danger to the participant as determined by the psychiatrist and, as stated in the consent, that 911 may be called if the clinician determines there is an emergency. The clinician will refer the participant to local resources should there be an emergency but will not provide ongoing care.

Potential Benefit

Knowledge gained from the study could potentially benefit patients in the future.

Participation in this study might lead to identification of clinically significant depression or clinically significant anxiety, enabling earlier therapy known to positively impact outcomes.

Adverse Events Reporting

Definitions

Term	Definition
Adverse Event (AE)	Any untoward medical occurrence, unintended disease or injury, or untoward clinical signs (including abnormal laboratory findings) in participants, users or other persons, whether or not related to the investigational Device (ISO 14155-1).
Serious Adverse Event (SAE)	Adverse event that a) Led to death, b) Led to serious deterioration in the health of the participant, that either resulted in 1) A life-threatening illness or injury, or 2) A permanent impairment of a body structure or a body function, or 3) In-patient or prolonged hospitalization, or 4) Medical or surgical intervention to prevent life-threatening illness or injury or permanent impairment to a body structure or a body function, c) Led to fetal distress, fetal death or a congenital abnormality or birth defect (ISO 14155-1).
Anticipated Serious Adverse Device Effect (ASADE)	An anticipated serious adverse Device effect (ASADE) is any SAE on health or safety or any life-threatening problem or death caused by, or associated with the Device, if that effect, problem, or death was previously identified in nature, severity, or degree of incidence in the investigational plan, informed consent, operator manual, other risk analysis documentation or regulatory application; or any other serious problem associated with a Device that relates to the rights, safety, or welfare of subjects.

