Unanticipated Serious Adverse Device Effect (USADE)	Any serious adverse effect on health or safety or any life-threatening problem or death caused by, or associated with, a Device, if that effect, problem, or death was not previously identified in nature, severity, or degree of incidence in the investigational plan or application (including a supplementary plan or application), or any other unanticipated serious problem

	associated with a Device that relates to the rights, safety, or welfare of participants 21 CFR 812.3(s).
--	--

Recording of AEs/ADEs and SAEs/SADEs

All suspected adverse events (AEs) will be evaluated and recorded in the participant’s study case report form. The AEs/ADEs/SAEs/SADEs may be observed by the investigator and/or clinical research staff or volunteered by the subject. All observed and volunteered adverse signs and symptoms, anticipated or unanticipated, regardless of severity or frequency will be recorded in the case histories (i.e. case report form). The reports of the AEs/ADEs/SAEs/SADEs will include the description of the event or symptom, date of onset, date of resolution, severity, anticipated or unanticipated, the relationship to the study Device, the action taken (if any), and the outcome. AEs/ADEs will be reported to the IRB only if the study clinicians, [name] and [name], determine that the event is possibly or definitely related to the Device. All SAEs/SADEs, anticipated or unanticipated, must be reported to the sponsor and reviewed by the IRB as soon as possible, but no later than 10 working days after the initial event was recorded. The study clinicians, [name] and [name], will review all adverse events to determine the severity and relationship to study Device.

Follow-up of Subjects after AEs

All reported AEs/ADEs/SAEs/SADEs should be followed until resolution of the event or until the subject’s participation in the study ends. Resolutions of the events should be documented in the appropriate case report form.

Data Analysis Plan

This is a prospective study with up to 100 subjects who meet the inclusion criteria and who do not meet any of the exclusion criteria.

The analysis set includes all enrolled subjects who provide a sample of their voice and are evaluated by a specialist. Device-related adverse events will be tabulated and analyzed.

Study Management

Investigator, Clinician, and Research Staff Selection

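### Adverse events are judged for relationship to the Device only, so non-serious events caused by the interview, survey or recording are recorded but not attributed to the procedure and do not reach the IRB

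*Protocol*

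**What the plan says.** **Risks named.** Under Potential Risks, the Protocol calls study risk minimal and names two harms: "The main potential risk to study participants is loss of confidentiality" and "Participants may feel discomfort answering questions or being interviewed".

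**What is collected.** Under Safety Endpoints, "Adverse events (AEs) and serious adverse events (SAEs) will be collected and reported from enrollment" through study completion. The definitions table makes an adverse event "Any untoward medical occurrence, unintended disease or injury, or untoward clinical signs", regardless of any link to the Device. The recording section adds: "All observed and volunteered adverse signs and symptoms, anticipated or unanticipated, regardless of severity or frequency will be recorded in the case histories".

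**How causality is judged and what goes to the IRB.** The same section lists the contents of an event report. The one causality item is relationship to the study Device, and the study clinicians' review covers severity and that same relationship. Adverse events go to the IRB only where the clinicians "determine that the event is possibly or definitely related to the Device". For serious events the rule differs: "All SAEs/SADEs, anticipated or unanticipated, must be reported to the sponsor and reviewed by the IRB", within a fixed number of working days.

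**The concern.** The causality question and the IRB filter both rest on the Device, but participants have little contact with the Device. They sit through a recorded psychiatric interview, complete a survey, and have their recordings stored. The one harm named under Potential Risks that could plausibly appear as a symptom comes from the interview.

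A filter built on Device relationship is therefore likely to remove the kind of non-serious event that this study is most likely to produce. At stake is the IRB's view of how participants tolerate the procedures while the study runs, and the ability to say at the end how many events the procedures caused. Diagnostic accuracy is not at stake.

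**Working it through.** No arithmetic applies, because the Protocol gives no event rate or reporting figure to reproduce. The check follows each named harm through the Protocol's own rules.

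**Step 1: where participants meet the Device.** Study Design and Procedures takes the Device input from the recorded SCID interview. Under Randomization, a research team member runs the audio through the Device, and neither participants nor clinicians receive the output. The closest a participant comes to the Device is being recorded or, if the audio cannot be scored, being asked for another sample. The output cannot upset a participant who never sees it.

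**Step 2: non-serious interview discomfort.**

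| Stage | Rule | Result |
|---|---|---|
| Case report form | All adverse signs and symptoms, any severity | Recorded |
| Safety endpoint | Adverse events collected, related to the Device or not | Collected |
| Causality | Relationship to the Device only | Interview has no category |
| IRB | Adverse events only if judged Device-related | Not sent |

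The event is captured. What is lost is its attribution and its route to the IRB.

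**Step 3: serious events caused by the interview.** All serious adverse events go to the sponsor and the IRB, with no causality condition. There is no gap here, so the restriction affects non-serious events only.

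**Step 4: loss of confidentiality.** A leaked recording or contact list is not in itself a medical occurrence, disease, injury or clinical sign, so it does not meet the adverse-event definition unless a medical event follows. Data Collection and Storage and Subject Confidentiality describe safeguards and access, but neither says how a breach is to be recorded. The nearest route is the wording in the definition of an anticipated serious adverse device effect that takes in "any other serious problem associated with a Device that relates to the rights, safety, or welfare of subjects", with a similar clause for unanticipated effects. Those clauses require the problem to be both serious and Device-associated. A leak of recruitment contact data would not obviously qualify.

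**Step 5: whether another document could settle this.** A statistical analysis plan may exist and could add tabulations. The causality item and the IRB filter, however, are fixed in the Protocol, and the filter is worded as a restriction.

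**The case against.** The strongest reply is that the system already sees what matters. Interview discomfort is recorded whatever its severity, the study clinicians review every adverse event, and serious events reach the IRB whatever their cause. Foreseen, mild discomfort in a study described as minimal risk need not go to an IRB case by case. This largely stands, and it limits the point to attribution and IRB reporting of non-serious events.

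The threshold also includes a possible relationship, and the interview audio is itself the Device input. A clinician could therefore treat discomfort at being recorded as possibly Device-related. That is a fair reading for some events. It leaves reporting to depend on how far each clinician stretches the word Device, and it does not help with distress caused by the questions themselves. A free-text description might mention the interview, but that is not a causality judgement that can be counted.

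On confidentiality, the Protocol places privacy on a separate track with coded identifiers, password protection and HIPAA safeguards, and keeping privacy incidents out of medical event counts is coherent. This too stands. A reader might infer that the Protocol bars reporting a breach to the IRB. It does not: the filter applies to adverse events, a breach as such is not one, and the text is silent. Procedures outside this document may cover it.

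**Conclusion.** The point holds for non-serious adverse events caused by study procedures. Followed as written, the Protocol records them, never attributes them to the procedure, and does not send them to the IRB. Every one of up to 100 participants is exposed to these procedures, but that counts exposure and not missed events; the number of events affected cannot be derived from the Protocol.

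A reader might infer that both named harms escape both the safety endpoint and the IRB, or that the study could report a clean safety result after repeated interview discomfort. The Protocol does not support either. Discomfort that is observed or volunteered is collected on the case report form, and serious events are reported regardless of cause. For confidentiality, the finding is only that no recording rule is stated for the risk ranked first, which is a clarification and secondary.

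The conclusion assumes that discomfort which is observed or volunteered counts as an adverse sign or symptom, and that clinicians read relationship to the Device in its ordinary sense. It is worth correcting before enrolment, but it does not touch the sensitivity and specificity endpoints.

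**What to change.** In Recording of AEs/ADEs and SAEs/SADEs, change the causality judgement to relationship to the Device or to a study procedure (interview, survey, recording). Record which of these applies, and apply the existing IRB reporting rule to either. Leave the rule for serious events as it is.

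As a secondary clarification, state that any loss of confidentiality is logged and listed beside the adverse events, without being counted as a medical event.

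The cost is one more relationship field on the case report form, a simple log for breaches, and slightly more IRB reports. The sample size, study procedures and accuracy analyses do not change.
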